10.3.2 NIS-LL (Neuropathy Impairment Score Lower-Limbs)

See Section 6.1.1 for numerical reassignment of visits.

Descriptive statistics (Mean, SD, Median, Minimum, Maximum, Q1, Q3 and N) of the following quantitative variables will be displayed:

- NIS-LL result (total score ranges from 0 to 88), assigned value for each visit.
- Increase for each visit (monthly unit change x month).
- To the extent possible, parametric (paired t-test) or non-parametric (Wilcoxon) statistical tests will be performed, depending on the sample distribution, to study whether there are differences in the unit change rate for pre- and post-treatment NIS-LL (total and subgroups).

10.3.3 FAP (Familiar Amyloidotic Polyneuropathy stage)

Frequencies (N. %) will be shown for the following qualitative variable:

- FAP (Yes / No)
- FAP result (Asymptomatic / Free ambulation / Supportive ambulation / Wheelchair-bound or bedridden)

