9. RESEARCH METHODS

9.1. Study design

Retrospective, multicenter, non-interventional, observational and descriptive study.

It will by no means interfere with the investigator's decision on the most appropriate medical care or treatment for the patient or carrier.

The variables collected are consistent with the objectives of the study and will be described in more detail in Section 9.3:

Primary objective	Primary variables
To determine the efficacy of tafamidis free acid 61 mg in ATTRv patients with neurologic involvement included in studies B3461028 and/or LTE (B3461045) in Spain through changes in the NIS scale at 12 months.	Neuropathy Impairment Score (NIS)
Secondary objectives	Secondary variables
To determine the efficacy of tafamidis 61 mg in ATTRv patients with neurologic involvement included in studies B3461028 and/or LTE (B3461045) in Spain using additional non-cardiac variables at 6, 12, 18, 24 and 36 months after the start of treatment.	
 - NIS at 6, 18, 24 and 36 months - NIS-LL, Norfolk QoL-DN, COMPASS-31 and FAP-RODs, FAP - % of patients who do not have stage progression in the PND score

PFIZER CONFIDENTIAL

	
 - % of patients responding to treatment (defined as <4p in NIS and <2p in NIS-LL) - R-R Range Variability - mBMI - Amplitude of the potentials measured in sural sensory and ulnar, tibial and peroneal motor NCS

To determine the efficacy of tafamidis free acid 61 mg in ATTRwt patients with neurological symptoms included in studies B3461028 and/or LTE (B3461045) in Spain, through non-cardiac variables at 6, 12, 18, 24 and 36 months after treatment initiation.
	
 - NIS, NIS-LL, Norfolk QoL-DN, COMPASS-31 and FAP-RODs, FAP - % of patients who do not have stage progression in the PND score - % of patients responding to treatment (defined as <4p in NIS and <2p in NIS-LL) - R-R Range Variability - mBMI. - Amplitude of the potentials measured in sural sensory and ulnar, tibial and peroneal motor NCS

To describe the extra-cardiac characteristics of ATTRv and ATTRwt patients included in studies B3461028 and/or LTE (B3461045) in Spain with mixed phenotype treated with tafamidis free acid 61 mg.
	
 - Demographic variables - Age of onset symptoms and at diagnosis - Neurological and extra-cardiac clinical variables

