6 METHODS FOR THE STATISTICAL ANALYSIS

The analysis methods to be used to achieve the study objectives and draw up the descriptive content for the variables are detailed below.

❖ UNIVARIATE ANALYSIS

Quantitative variables will be described with centralization and scattering measures (mean, SD (standard deviation), median, minimum, maximum, Q1 (first quartile), Q3 (third quartile and N).

Qualitative variables will be described by absolute and relative frequencies. Two columns of percentages will be presented: Total Percentage (Total %) and Valid Percentage (Valid %):

- Total Percentage (%): Percentage of the sum of valid responses plus missing values, i.e. of the total of the sample under study.
- Valid percentage (Valid %): Percentage of total valid responses, i.e. with data on the variable.

In subgroup analyses, only the valid % with respect to the total for each group will be presented.

For questions with more than one answer option, **multiple response** tables will be shown. Two percentage column will be shown in these tables:

- Total percentage (%) Percentage of the sum of valid responses plus missing values, i.e. of the total of the sample under study. Since it is multiple choice, the sum of percentages does not have to be 100 (the percentage may be exceeded).
- Valid percentage (%) Percentage of the number of patients with at least one given answer from among the possible answers. Since it is multiple choice, the sum of percentages does not have to be 100 (the percentage may be exceeded).

Missing data will not be attributed and will be left as lost data.

Statistical analysis of variables collected in the study will be performed using the SPSS statistical program.

NOTE 1: Due to the small number of patients available in the study, no comparisons will be made and the associated p-value will not be shown. Only descriptive analyses will be presented.

NOTE 2: The texts collected in open fields will not be grouped, other than to standardize format and spelling. If desired, any grouping must be performed by the sponsor and as an additional table to the description of what is included in the database.

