10 VARIABLES AT FOLLOW-UP

Results will be shown at Months **6, 12, 18, 24 and 36 after treatment initiation** (see section 6.1 with re-assignment of visits).

Analyses will be performed on the total population and subgroup based on genotype (ATTRv and ATTRwt). Descriptive analyses will be presented with no comparisons between genotype groups.

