10.4 Neurophysiological variables

Frequencies (N. %) will be shown for the following qualitative variables:

- Nerve conduction study (EMG)
 - Axonal / Demyelinating (Altered / Unaltered)
- Sudoscan Electrocuteaneous Conductance (ECC):
- RR Interval Variability (Altered / Unaltered)
 - Contingency (descriptive) table of RR interval variability with pre-treatment and follow-up data.

Descriptive statistics (Mean, SD, Median, Minimum, Maximum, Q1, Q3 and N) of the following

quantitative variables will be displayed:

- Nerve conduction study (EMG)
 - Ulnar / peroneal CMAP amplitude (mV)
 - Ulnar / Sural SNAP amplitude (μ V)
- Sudoscan Electrocutaneous Conductance (ECC):
 - Hands result (μ S)
 - Feet result (μ S)
- Change, difference, from values indicated at start of treatment:
 - Ulnar / peroneal CMAP amplitude
 - Ulnar / Sural SNAP amplitude
 - CCE by Sudoscan (hands and feet)

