12.2 Secondary objectives

12.2.1 Secondary objective 1

“To determine the efficacy of Tafamidis 61 mg in ATTRv patients with neurologic involvement included in studies B3461045 and/or LTE (B3461045) in Spain using additional non-cardiac variables at 6, 12, 18, 24 and 36 months after the start of treatment”

NOTE: ATTRv patients are considered to be those who have indicated “Mutation” in the genotype (“Data related to the disease at diagnosis”).

Results will be presented in each month (6, 12, 18, 24 and 36) (see section 6.1 visit reassignment).

Secondary objective 1 [sic: 2] variables:

- NIS at 6, 18, 24 and 36 months (see section 10.3.1)
- NIS-LL (section 10.3.2), Norfolk QoL-DN (section 10.5.1), COMPASS-31 (section 10.5.3) and FAP-RODs (section 10.5.2), FAP (section 10.3.3)
- % of patients whose stage does not progress in the PND score (section 10.3.4). N and % of patients whose stage does not progress in the PND will also be obtained, referring to patients who do not change to higher stages compared to the start of treatment.
- % of treatment responders. N and % of responder patients will be calculated for this objective, with responder being defined as:
 - **NIS:** Results will be presented in each month, defining responder as:
 - change at 6 months from baseline <2p in NIS, patients who have achieved less than 2 points in the NIS.
 - change at 12 months from baseline <4p in NIS, patients who have achieved less than 4 points in the NIS.
 - change at 18 months from baseline <6p in NIS, patients who have achieved less than 6 points in the NIS.
 - change at 24 months from baseline <8p in NIS, patients who have achieved less than 8 points in the NIS.
 - change at 36 months from baseline <12p in NIS and, patients who have achieved less than 12 points in the NIS.

Patients who do not meet the previous condition in each month will be considered non-responders. If complete data is not available, the value will be left as missing.

- **NIS-LL:** Results will be presented in each month, defining responder as:
 - change at 6 months from baseline <1p in NIS-LL, patients who have achieved less than 1 point in the NIS-LL at Month 6.
 - change at 12 months from baseline <2p in NIS-LL, patients who have achieved less 2 points in the NIS-LL at Month 12.
 - change at 18 months from baseline <3p in NIS-LL, patients who have achieved less than 3 points in the NIS-LL at Month 18.

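### FAP stage is a secondary efficacy variable, but the SAP plans only stage frequencies at each month and no within-patient comparison with the start of treatment

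*SAP*

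**What the plan says.** Protocol 9.1 names FAP among the secondary variables for ATTRv ("NIS-LL, Norfolk QoL-DN, COMPASS-31 and FAP-RODs, FAP") and for ATTRwt ("NIS, NIS-LL, Norfolk QoL-DN, COMPASS-31 and FAP-RODs, FAP"). SAP 12.2.1 and 12.2.2 repeat the list and send FAP to one place only: "COMPASS-31 (section 10.5.3) and FAP-RODs (section 10.5.2), FAP (section 10.3.3".

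SAP 10.3.3 plans N and % for an undefined FAP yes/no item and for "FAP result (Asymptomatic / Free ambulation / Supportive ambulation / Wheelchair-bound or bedridden". The timing comes from SAP 10: "Results will be shown at Months 6, 12, 18, 24 and 36 after treatment initiation". SAP 6 adds "Missing data will not be attributed and will be left as lost data" and gives only the valid percentage in subgroup tables. SAP 6.1.2 keeps categorical variables out of the interpolation and carry-forward procedure of 6.1.1.

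The two closest variables are treated differently. For PND, SAP 12.2 counts patients without stage progression, "referring to patients who do not change to higher stages compared to the start of treatment". For R-R variability, SAP 10.4 plans a "Contingency (descriptive) table of RR interval variability with pre-treatment and follow-up data".

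**The concern.** The study hypothesis is about slowing progression of polyneuropathy, and progression is a change within a patient. A stage distribution at each month, set beside a separate baseline distribution (SAP 9.1.3), compares marginal totals and cannot say which patients moved.

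The patients behind each month can also differ. Eligibility secures 12 months of neurological follow-up and no more, the data come from routine visits, and Protocol 9.9 itself warns that follow-up data may be scarce. At Months 18, 24 and 36, a change in the FAP percentages may reflect who has a value as much as any change in stage. What is at stake is the reading of one secondary variable in two groups of about 10 patients.

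**Working it through.** There is no planned figure to reproduce. The SAP gives an expected 10 ATTRv and 10 ATTRwt patients (SAP 4), with no sample-size calculation and no dropout rate.

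**1. What each secondary efficacy variable receives at follow-up**

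| Variable | Comparison with the start of treatment |
|---|---|
| NIS | Change per month, plus a per-patient listing (10.3.1) |
| NIS-LL, Norfolk QoL-DN, FAP-RODS, COMPASS-31 | Increase per visit (10.3.2, 10.5) |
| mBMI | Change from baseline (10.2) |
| NCS amplitudes | Change for ulnar, peroneal and sural; nothing for tibial (10.4) |
| PND | Non-progression rate (12.2.1, 12.2.2) |
| R-R variability | Before-and-after table (10.4) |
| FAP | None (10.3.3) |

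The paired tests that close 12.2.1 and 12.2.2 cover numeric variables only. The listing in 6.1.2 serves to assign visits to months and is not a results table.

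**2. With complete data (assumed)**

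Take 6 patients at stage 1 and 4 at stage 2. If nobody moves, the later table reads 6 and 4. If two worsen and two improve, it reads 6 − 2 + 2 = 6 and 4 + 2 − 2 = 4. The table is the same, but progression is 0/10 in one case and 2/10 in the other.

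**3. With some patients unobserved (assumed)**

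Let a patients start at stage 1 and b = 10 − a at stage 2. Let k move from stage 1 to stage 2, let m of the baseline stage-2 patients have no value, and let nobody improve.

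- Baseline share at stage 2 or above: b/10.
- Later valid share: (b − m + k)/(10 − m).
- The later share is lower when k < m × a/10. With k = 1 this means m > 10/a.

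Smallest m that gives a fall with k = 1:

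| a / b | m | Baseline | Later, valid | Not progressed, paired |
|---|---|---|---|---|
| 5 / 5 | 3 | 5/10 = 50.0% | 3/7 = 42.9% | 6/7 = 85.7% |
| 6 / 4 | 2 | 4/10 = 40.0% | 3/8 = 37.5% | 7/8 = 87.5% |
| 7 / 3 | 2 | 3/10 = 30.0% | 2/8 = 25.0% | 7/8 = 87.5% |
| 8 / 2 | 2 | 2/10 = 20.0% | 1/8 = 12.5% | 7/8 = 87.5% |

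The falls run from 2.5 to 7.5 percentage points. Each occurs although one patient worsened and none improved.

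**4. What a paired rate does and does not repair**

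In the 7/3 case the paired rate is 7/8 = 87.5%, which shows the one progression. The two unobserved patients remain unknown. If both progressed, the rate over all ten is 7/10 = 70%; if neither did, it is 9/10 = 90%. Pairing removes the artefact of changing patients but not selective loss.

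**5. Feasibility**

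The evaluability check in SAP 5 requires a FAP value before or at inclusion for every patient. The four categories are the same at baseline (9.1.3) and at follow-up (10.3.3).

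**The case against.** The strongest objection is that PND already supplies the answer. On the SAP's labels in 9.1.4, PND I and II need no support, IIIA and IIIB need it, and IV is wheelchair or bed. A move from FAP stage 1 to 2, or from 2 to 3, should therefore also raise the PND level. This largely stands and is the main reason the point is minor. It does not close the gap. Moves from I to II or from IIIA to IIIB count as PND progression with no change in FAP, so the FAP rate cannot be read off the PND rate. The follow-up PND categories in 10.3.4 are also the four FAP categories and do not match the six baseline PND levels, so the PND rate needs reconciling first.

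The study is descriptive, and the protocol asks for non-progression on PND only. A reader might infer that the SAP departs from the protocol here. It does not: the protocol lists FAP as a bare variable.

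A reader might also infer that the FAP table is likely to show a false improvement. The documents do not support this. They give no attrition figure and no sign that worse-stage patients are lost first. The protocol dates the switch of all extension-study patients to 61 mg from an addendum of 20 July 2018, almost 43 months before the protocol date of 17 February 2022, and SAP 5 also accepts 80 mg start dates. Month 36 values are therefore plausible for many patients. The illustrated falls are smaller than the weight of one patient in ten (10 points), and a fall from 10 to 8 patients would be visible in the counts.

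Nor is FAP the only named variable without a comparison: tibial amplitude has no planned summary either.

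**Conclusion.** The point holds as a minor gap in the analysis. For FAP the SAP plans no within-patient comparison with the start of treatment, in either genotype. This follows from the text and needs no assumption. That the percentages can fall while patients worsen is a matter of arithmetic: with 10 patients, one progression and two or three unobserved stage-2 patients are enough. The stage splits and the missing counts are assumed, so the 30% to 25% example shows what is possible and does not estimate a bias. The exposure is mainly after Month 12, because eligibility limits loss before then, although FAP may also go unrecorded at a routine visit. The primary NIS result is not affected.

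**What to change.** In SAP 10.3.3, 12.2.1 and 12.2.2, apply to FAP the rule already used for PND. By genotype and month, give the N and % of patients whose FAP stage is not higher than at the start of treatment, among those with both values. Add the number without a value at each month and their baseline stage. State that the paired rate does not correct for selective loss.

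Full four-by-four tables are not needed: five months for the total population and two genotypes would make 5 × 3 = 15 sparse tables. One compact table of worsened, unchanged, improved and missing, or a per-patient FAP listing, is enough. Reconcile the PND categories in 9.1.4 and 10.3.4 at the same time, so that the two rates can be read together.

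The cost is one descriptive table or listing from data already collected, with no test and no new variable.

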10.3.4 PND (Polyneuropathy Disability Score)

Frequencies (N. %) will be shown for the following qualitative variable:

- PND (Yes / No)
- PND result (Asymptomatic / Free ambulation / Supportive ambulation / Wheelchair-bound or bedridden)

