NIS (Neuropathy Impairment Score) is a clinically important, sensitive measure of individual neurological function, assessing sensory function, reflexes, and muscle weakness			
NIS-LL			
NIS-LL (Neuropathy Impairment Score Lower Limbs) is a clinically important, sensitive measure of neurological function in individuals, assessing sensory function, reflexes, and muscle weakness of the lower limbs			
PND	Result	Medical Record	The investigator will collect the data in the CRF reflecting the information included in the medical record or calculated from the medical record data
PND (Polyneuropathy disability score) is a simple staging system according to the degree of neuropathic dysfunction and its impact on ambulation			
FAP	Result	Medical Record	
FAP (Family Amyloidotic polyneuropathy stage) is a staging system based on symptom severity and disease progression			
NCS (EMG): sural sensory, ulnar, tibial and peroneal nerves	Result	Medical Record	
CCE - Sudoscan (feet and hands)			The investigator will collect the data in the CRF reflecting the information included in the medical record
Electrochemical Cutaneous Conductance allows us to measure autonomic sudomotor function in a non-invasive, rapid and accurate manner			
CVR-R			
The coefficient of variation of the R-R interval is a measure of cardiovascular autonomic dysfunction. It is calculated as the standard deviation percentage of the R-R intervals divided by their mean			

Norfolk QoL-DN	Result	Medical Record	
Norfolk Quality of Life Questionnaire for Diabetic Neuropathy is a standardized and validated instrument that assesses the effect of polyneuropathy on the functionality and quality of life of the individual			
FAP-RODS			The investigator will collect the data in the CRF reflecting the information included in the medical record
FAP-RODS (Familial Amyloid Polyneuropathy Specific Rasch-Built Overall Disability Scale) is a questionnaire that assesses the effect of neuropathy on daily activities	Result	Medical Record	
COMPASS-31			
COMPASS-31 (Composite Autonomic Symptom Score 31) is a questionnaire designed to assess the severity and functional ability in patients with autonomic dysfunction			
Proteinuria			
Albuminuria/microalbuminuria levels	Result	Medical Record	The investigator will collect the data in the CRF reflecting the information included in the medical record
eGFR (estimated Glomerular Filtration Rate)			

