4 STUDY POPULATION

The current study population consists of ATTRv and ATTRwt patients who have participated in studies B3461028 and B3461045 in Spain, with cardiac and neurologic involvement receiving or who have received Tafamidis free acid 61 mg for at least 12 months, and who are in neurological follow-up for no less than 12 months. According to the protocol, patients who meet the inclusion criteria are estimated to be: 10 with ATTRv and 10 with ATTRwt.

Individuals participating in the TRAMA study must meet all of the inclusion and none of the exclusion criteria.

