6.1.2 Categorical variables at follow-up and all other numerical variables

For categorical variables, the procedure explained above cannot be performed; as such, for these variables, a listing of the treatment start date (or the closest date) and the date of the follow-ups recorded will be sent for subsequent assignment to the corresponding month. This would also apply to all other numerical variables not covered in the previous section (e.g. BMI, albumin, etc.), as there will be no weighted increase for these variables over the visits.

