9.1 Neurological variables

9.1.1 *NIS (Neuropathy Impairment Score)*

Descriptive statistics (Mean, SD, Median, Minimum, Maximum, Q1, Q3 and N) of the following quantitative variable will be shown:

- NIS result (total score ranges from 0 to 244)

9.1.2 *NIS-LL (Neuropathy Impairment Score Lower-Limbs)*

Descriptive statistics (Mean, SD, Median, Minimum, Maximum, Q1, Q3 and N) of the following quantitative variable will be shown:

- NIS-LL result (total score ranges from 0 to 88)

9.1.3 *FAP (Familiar Amyloidotic Polyneuropathy stage)*

Frequencies (N. %) will be shown for the following qualitative variable:

- FAP result (Asymptomatic / Free ambulation or stage 1 / Supportive ambulation or stage 2 / Wheelchair-bound or bedridden or stage 3)

9.1.4 *PND (Polyneuropathy Disability Score)*

Frequencies (N. %) will be shown for the following qualitative variable:

- PND result (Asymptomatic / I Sensory disturbances, normal gait / II Sensory disturbances, altered gait not requiring support / IIIA Gait requiring support / IIIB Gait requiring two supports / IV Wheelchair or bedside)

9.2 **Neurophysiological variables**

Frequencies (N. %) will be shown for the following qualitative variables:

- Nerve conduction study (EMG)
 - Axonal / Demyelinating (Altered / Unaltered)
- Sudoscan Electrocuteaneous Conductance (ECC):
- RR Interval Variability (Altered / Unaltered)

Descriptive statistics (Mean, SD, Median, Minimum, Maximum, Q1, Q3 and N) of the following quantitative variables will be displayed:

- Nerve conduction study (EMG)
 - Ulnar / peroneal CMAP amplitude (mV)
 - Ulnar / Sural SNAP amplitude (μ V)
- Sudoscan Electrocuteaneous Conductance (ECC):
 - Hands result (μ S)
 - Feet result (μ S)

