NOTE: ATTRwt patients are considered to be those who have indicated “Wildtype” in the genotype (“Data related to the disease at diagnosis”).

Results will be presented in each month (6, 12, 18, 24 and 36) (see section **Error! Reference source not found.** visit reassignment).

Secondary objective 1 [sic: 2] variables:

- NIS (see section 10.3.1), NIS-LL (section 10.3.2), Norfolk QoL-DN (section 10.5.1), COMPASS-31 (section 10.5.3) and FAP-RODs (section 10.5.2), FAP (section 10.3.3)
- % of patients whose stage does not progress in the PND score (section 10.3.4). N and % of patients whose stage does not progress in the PND will also be obtained, referring to patients who do not change to higher stages compared to the start of treatment.
- % of treatment responders. N and % of responder patients will be calculated for this objective, with responder being defined as:
 - change at 6 months from baseline (<2p in NIS and <1p in NIS-LL), patients who have achieved less than 2 points in the NIS and simultaneously less than 1 point in the NIS-LL at Month 6.
 - change at 12 months from baseline (<4p in NIS and <2p in NIS-LL), patients who have achieved less than 4 points in the NIS and simultaneously less than 2 points in the NIS-LL at Month 12.
 - change at 18 months from baseline (<6p in NIS and <3p in NIS-LL), patients who have achieved less than 6 points in the NIS and simultaneously less than 3 points in the NIS-LL at Month 18.
 - change at 24 months from baseline (<8p in NIS and <4p in NIS-LL), patients who have achieved less than 8 points in the NIS and simultaneously less than 4 points in the NIS-LL at Month 24.

- change at 36 months from baseline (<12p in NIS and <6p in NIS-LL), patients who have achieved less than 12 points in the NIS and simultaneously less than 6 points in the NIS-LL at Month 36.
- R-R Range Variability (section 10.4)
- mBMI (section 10.2).
- Amplitude of the potentials measured in sural sensory and ulnar, tibial and peroneal motor NCS (section 10.4)

To the extent possible, parametric (paired t-test) or non-parametric (Wilcoxon) statistical tests will be performed, depending on the sample distribution, to study whether there are differences in the unit change rate for pre- and post-treatment previous numeric variables (total and subgroups).

12.2.3 Secondary objective 3

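### Three SAP definitions do not match their secondary endpoints: follow-up PND uses the FAP categories, the Month-36 NIS-LL responder repeats the composite rule, and tibial amplitude is not summarised

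*SAP*

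**What the plan says.** **PND.** Protocol 9.3 treats PND and FAP as separate variables; PND "is a simple staging system according to the degree of neuropathic dysfunction and its impact on ambulation". SAP 9.1.4 records baseline PND in six levels: asymptomatic, I, II, IIIA, IIIB and IV. Its wording separates the two III grades ("IIIA Gait requiring support / IIIB Gait requiring two supports"). At follow-up, SAP 10.3.4 gives "PND result (Asymptomatic / Free ambulation / Supportive ambulation / Wheelchair-bound or bedridden", while 10.3.3 just above it gives "FAP result (Asymptomatic / Free ambulation / Supportive ambulation / Wheelchair-bound or bedridden". In SAP 12.2.1 and 12.2.2 the endpoint is the percentage "of patients whose stage does not progress in the PND score (section 10.3.4", with the rule stated as "referring to patients who do not change to higher stages compared to the start of treatment". For categorical variables, SAP 6.1.2 says only that a listing of dates "will be sent for subsequent assignment to the corresponding month".

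**NIS-LL responder.** The change log in SAP 2.1 says version 2.0 added responder analyses for NIS and for NIS-LL separately under secondary objective 1. In 12.2.1 the NIS-LL list uses NIS-LL alone at Months 6 to 24, with limits of 1, 2, 3 and 4 points. At Month 36 it requires a change below 12 on NIS and below 6 on NIS-LL.

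**Nerve conduction.** The endpoint in Protocol 9.1 and SAP 12.2.1 and 12.2.2 names sural sensory and ulnar, tibial and peroneal motor amplitudes; the SAP refers to 10.4 for it. Protocol 9.3 lists all four nerves for collection. SAP 9.2 and 10.4 summarise ulnar and peroneal CMAP and ulnar and sural SNAP.

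**The concern.** A non-progression endpoint needs the same ordered scale at both time points. Here the start-of-treatment value has six levels and the follow-up value four, and the SAP gives no mapping between them. If baseline is collapsed to the four categories, some real worsening is counted as stability, and the endpoint adds little to FAP stage. If baseline stays at six levels, the SAP has no rule for the comparison. Non-progression in PND is a protocol secondary variable in both genotype groups.

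The Month-36 NIS-LL-only rate, as written, is the composite rate under another name. It cannot be read as a continuation of Months 6 to 24, and it goes missing whenever NIS is missing, even if NIS-LL is known.

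For nerve conduction, one component of a four-nerve endpoint has no value or change table in the section the endpoint cites.

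In a descriptive study the category lists and responder rules are the analysis, so a programmer following this text would produce tables that do not answer the stated endpoints.

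**Working it through.** The plan states no figure for any of these points, so the check is a comparison of texts followed by counting.

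**1. PND**

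The SAP gives no mapping; the one below is an assumption drawn from the gait descriptions in 9.1.4, where I and II need no support and IIIA and IIIB do.

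| Baseline level (9.1.4) | Follow-up category (10.3.4) | Upward moves possible | Hidden |
|---|---|---|---|
| Asymptomatic | Asymptomatic | 5 | 0 |
| I | Free ambulation | 4 | 1 (to II) |
| II | Free ambulation | 3 | 0 |
| IIIA | Supportive ambulation | 2 | 1 (to IIIB) |
| IIIB | Supportive ambulation | 1 | 0 |
| IV | Wheelchair or bedridden | 0 | 0 |

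- Total upward moves: 6 × 5 / 2 = 15. Hidden: 2. Detectable: 13.
- One-step moves: 5. Hidden: 2 (I to II, IIIA to IIIB). Detectable: 3.
- Direction: the mapping preserves order, so it can never turn a non-progressor into a progressor. The error runs only towards higher non-progression.
- Effect per hidden progressor: 100/n percentage points. SAP section 4 has patients "estimated to be: 10 with ATTRv and 10 with ATTRwt", so 100/10 = 10 points. If only some have PND data (assumed values): 100/8 = 12.5 points and 100/5 = 20 points.

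**2. NIS-LL-only responder (SAP 12.2.1)**

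| Month | NIS-LL list | Combined list |
|---|---|---|
| 6 | NIS-LL < 1 | NIS < 2 and NIS-LL < 1 |
| 12 | NIS-LL < 2 | NIS < 4 and NIS-LL < 2 |
| 18 | NIS-LL < 3 | NIS < 6 and NIS-LL < 3 |
| 24 | NIS-LL < 4 | NIS < 8 and NIS-LL < 4 |
| 36 | NIS < 12 and NIS-LL < 6 | NIS < 12 and NIS-LL < 6 |

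- Four of the five lines use NIS-LL alone; the fifth is the combined rule.
- The series is 1/6 = 2/12 = 3/18 = 4/24, or 1 point per 6 months. At Month 36 this gives 36/6 = 6 points, already the NIS-LL part of the combined rule.
- Example: with NIS +13 and NIS-LL +5, a patient satisfies 5 < 6 but is a non-responder as written because 13 ≥ 12.
- Each such patient lowers the Month-36 rate by 100/n: 10 points at n = 10, and 12.5 or 20 at the assumed n = 8 or 5. Eligibility requires only 12 months of neurological follow-up, so n at Month 36 is uncertain.

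**3. Nerve conduction**

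- Endpoint: sural sensory; ulnar, tibial and peroneal motor.
- Summarised in 9.2 and 10.4: sural and ulnar SNAP; ulnar and peroneal CMAP.
- In the endpoint but not summarised: tibial motor, 1 of 4. Summarised but not in the endpoint: ulnar SNAP.
- The gap is the same at baseline and follow-up, so no change from start of treatment is listed either.

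**The case against.** The case against accepts the mismatches but disputes their weight.

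- *The PND list in 10.3.4 may be a pasted label.* The endpoint rule lies in 12.2, and follow-up data may hold six levels. Inflation needs both four-level follow-up coding and a collapsed baseline, and the CRF is not available to settle this. That stands as a condition on the bias. It does not rescue the text: the endpoint cites 10.3.4, and neither that section nor 6.1.2 restores the six levels.
- *The counts 2 of 5 and 2 of 15 are not frequencies, and 10 points per patient is simply 1/n.* Correct. They show which moves are lost and what each is worth, not how many patients are affected.
- *A six-level baseline against four categories is coarse rather than impossible to compare.* Fair, given the mapping above. The SAP does not state that mapping, so the comparison is unspecified.
- *The NIS-LL intent is already clear.* It is, from the list's title, its other four lines and the change log. The Month-36 line still gives a different answer if programmed as written.
- *Tibial is named in 12.2, and section 6 gives general statistics for quantitative variables.* True, so omission is not certain. But the lists in 9.2 and 10.4 leave it out, and 10.4 is where the endpoint sends the reader.
- *The second and third points are minor.* Agreed: they are consistency edits. PND carries the weight.

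**Conclusion.** The concern holds on all three counts. The main one is PND: a six-level baseline is set against a four-category follow-up list identical to FAP, for a protocol secondary endpoint in both genotype groups. The mismatch needs no assumption. Its consequence, the loss of I to II and IIIA to IIIB worsening, rests on the mapping above and on 10.3.4 being applied as written with baseline collapsed. The number of patients affected cannot be derived from the documents.

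The Month-36 NIS-LL-only line is wrong in 1 of 5 places and affects ATTRv only; secondary objective 2 uses only the composite rule, and the protocol's composite responder is untouched. Tibial amplitude lacks a listed summary in both genotype groups.

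These should be corrected before the tables are produced. The primary endpoint, NIS change at 12 months, is not affected.

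**What to change.** 1. **SAP 10.3.4:** replace the four categories with the six levels of 9.1.4 and apply the existing rule of 12.2.1 and 12.2.2 to them. If the follow-up CRF holds only four categories, collapse baseline to the same four, print the mapping, and state that worsening within I/II and within IIIA/IIIB cannot be seen.
2. **SAP 12.2.1, NIS-LL list, Month 36:** require a change below 6 points on NIS-LL alone. Leave the combined list as it is.
3. **SAP 9.2 and 10.4:** add tibial CMAP amplitude, as value and as change from start of treatment, if it was collected. If not, say so and amend the endpoint in 12.2.1 and 12.2.2.

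The cost is three wording changes and one check of the follow-up CRF for PND level and tibial amplitude, with no new data collection. The PND non-progression rate may become less favourable. Among patients with both scores, the Month-36 NIS-LL-only rate can only stay the same or rise.
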